For each marketplace condition, participants will complete 10 iterations of the ETM task in ascending order. The prices for menthol cigarettes on the ETM will be set at: \$0.12, \$0.25, \$0.50, \$1.00, \$2.00, \$4.00, \$8.00, and \$16.00 and \$32.00 per cigarette. During one task iteration, menthol cigarettes will be eliminated from the marketplace to simulate a menthol cigarette ban. The costs for the other products will reflect average prices in NC and will not change during the task. For each task iteration, participants will receive individually-tailored account balances approximately equal to the money they would spend on cigarettes for seven days. They can

purchase as many or few products as their account balance allows. Participants are not required to buy products from the ETM or can buy nicotine gum if they prefer to abstain. If they do not buy products from the ETM and do not use tobacco products during the field assessment (biochemically-verified), then they will receive their ETM account balance at Virtual Visit 6. This payment is delayed to reduce the likelihood that they will use this money to buy their preferred brand menthol cigarettes, thus decreasing the validity of the ETM task.

Participants will be instructed to use only the products purchased from the ETM during the subsequent 7-day period after Virtual Visit 5 and told that we will assess adherence by self-report, product accountability, and biochemical verification. The field assessment validates the ETM task by having participants use the products in the real world, simulating the different regulatory environments. Actual product use enables us to measure their subjective experiences such as withdrawal, craving, or product satisfaction as well as assess changes in carbon monoxide exposure, a biomarker of harm, when using products other than menthol cigarettes. We will conduct between-subjects analyses comparing these secondary outcomes by marketplace condition.

In-Person Lab Visit 2

In-Person Lab Visit 2 will be completed up to 48 hours after completing Virtual Visit 5. Participants will complete the COVID screener within 24 hours of their Lab visit via email or phone. Research staff will wear personal protective equipment during the visit including face masks and gloves. The participants will be required to wear facemasks when interacting with the staff. Temperature checks will be conducted immediately upon arrival using a thermal heat scanner.

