Participants will provide CO readings be at least 6-feet away from other people, including the research staff, while they have their masks off.

Participants will be given the products they purchased during the ETM task and will be instructed to only use these products for the next seven days. They will also be given a urine collection cup and instructions for sample collection.

Virtual Visit 6

Participants will complete Virtual Session 6 seven days after completing In-Person Lab Visit 2. They will bring a first morning void urine sample, which will be banked for future biomarker analysis (e.g., total nicotine equivalents).

The following baseline assessments will be administered as an interview and entered into REDCap by the interviewer:

1. Timeline Follow Back (TLFB) Questionnaire which will assess past tobacco and nicotine product use since Virtual Visit 5.

The following surveys will be self-administered using REDCap:

1. Tobacco Policy Questionnaire
2. Minnesota Nicotine Withdrawal Scale

3. Questionnaire of Smoking Urges-Brief – Usual Brand Cigarette
4. Product Evaluation Scale
5. Perceived Health Risks Scale
6. Tobacco Product Interest Scale

Participants will complete the ETM task under the same marketplace condition from which they received their field assessment products. Exploratory pre-post field assessment analyses will examine how actual use of the products affects subsequent purchasing of those products.

Research staff will conduct in-depth interviews with the participants to assess the following constructions: 1) decision-making during the ETM task; 2) use of alternative products during the field assessment; 3) product risk perceptions and; 4) opinions regarding possible tobacco control policies.

In-Person Lab Visit 3

In-Person Lab Visit 3 will be completed up to 48 hours after completing Virtual Visit 6. Participants will complete the COVID screener within 24 hours of their Lab visit via email or phone. Research staff will wear personal protective equipment during the visit including face masks and gloves. The participants will be required to wear facemasks when interacting with the staff. Temperature checks will be conducted immediately upon arrival using a thermal heat scanner. Participants will bring a first void urine sample and all of their used/unused products.

Participants will provide CO readings at least 6-feet away from other people, including the research staff, while they have their masks off.

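### The only post-field CO reading may be taken up to 48 h after the product-only week ends, and no product-use record covers that gap

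*Combined protocol and SAP*

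**What the plan says.** All references are to the combined protocol and SAP.

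- **Product-only period.** Under In-Person Lab Visit 2, participants receive their products and "will be instructed to only use these products for the next seven days". Under Virtual Visits 2-5, the same instruction applies "during the subsequent 7-day period after Virtual Visit 5". These start points can differ, because "In-Person Lab Visit 2 will be completed up to 48 hours after completing Virtual Visit 5".
- **End of the field week.** "Participants will complete Virtual Session 6 seven days after completing In-Person Lab Visit 2". The TLFB at that visit covers use since Virtual Visit 5, and the in-depth interview takes place at the same visit.
- **CO.** "In-Person Lab Visit 3 will be completed up to 48 hours after completing Virtual Visit 6". CO is read there. No TLFB or other product-use question is listed for that visit.
- **Uses of CO.** Virtual Visits 2-5 justifies the field week partly as a way to "assess changes in carbon monoxide exposure, a biomarker of harm, when using products other than menthol cigarettes", and says the secondary outcomes it describes will be compared between participants by marketplace condition. Product adherence uses a reading below 6 ppm to confirm a report of no combusted tobacco.
- **Urine.** Under Virtual Visit 6: "They will bring a first morning void urine sample, which will be banked for future biomarker analysis". Under In-Person Lab Visit 3: "Participants will bring a first void urine sample and all of their used/unused products".
- **Payment.** Under Virtual Visits 2-5, participants who buy nothing and are biochemically verified as not using tobacco receive their account balance at Virtual Visit 6.

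**The concern.** The CO reading is meant to describe the field week, but it may be taken after that week has closed. Expired CO reflects recent smoking, so what happens in the hours just before the reading matters most, and the plan does not record those hours when Lab Visit 3 is late.

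Two uses of CO are at stake:

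- **Verification.** The self-report covers the period up to Virtual Visit 6, while the reading covers a later one. A participant who truthfully reported no combusted tobacco and then smoked in the gap could read 6 ppm or more and be left unverified.
- **Comparison by condition.** Smoking in the gap that is unrelated to the assigned products would add the same kind of exposure in every condition and pull the CO contrast toward zero.

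Neither problem can be repaired in the analysis, because product use in the gap is not collected.

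**Working it through.** The plan states no figure to reproduce, so the check is the visit timeline followed by an illustration of CO decay.

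**Step 1. Timeline, in hours from Virtual Visit 5 (VV5 = 0).** The windows come from the visit sections.

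- Lab Visit 2 (LV2) = 0 to 48
- Virtual Visit 6 (VV6) = LV2 + 7 × 24 = LV2 + 168
- Lab Visit 3 (LV3) = VV6 + 0 to 48

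| VV5 to LV2 | VV6 to LV3 | VV6 on day | LV3 on day | LV3 after seven days from LV2 | LV3 after seven days from VV5 | Hours before CO with no TLFB |
|---|---|---|---|---|---|---|
| 0 h | 0 h | 7 | 7 | 0 h | 0 h | 0 h |
| 0 h | 48 h | 7 | 9 | 48 h | 48 h | 48 h |
| 48 h | 0 h | 9 | 9 | 0 h | 48 h | 0 h |
| 48 h | 48 h | 9 | 11 | 48 h | 96 h | 48 h |

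Counting from Lab Visit 2, the CO reading falls 0 to 48 h after the product-only period. Counting from Virtual Visit 5, it falls 0 to 96 h after. Under either count, the last 0 to 48 h lie outside any TLFB.

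**Step 2. Does anything else cover the gap?** Product adherence assesses use of products not bought in the task through the TLFB and the interview, both at Virtual Visit 6. The count of returned products at Lab Visit 3 does span the gap. It covers study products only, so it cannot show own-brand smoking or separate the gap from the field week.

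**Step 3. How much of the Virtual Visit 6 CO level survives the gap?** The documents give no half-life, so 2 to 8 h is assumed. With no smoking in the gap, the share of the excess remaining is 2^(−t / half-life).

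| Assumed half-life | After 12 h | After 24 h | After 48 h |
|---|---|---|---|
| 2 h | 1.6% | 0.02% | < 0.01% |
| 4 h | 12.5% | 1.6% | 0.02% |
| 6 h | 25.0% | 6.3% | 0.4% |
| 8 h | 35.4% | 12.5% | 1.6% |

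For example, at 8 h and 24 h: 2^(−24/8) = 2^(−3) = 12.5%. At 8 h and 48 h: 2^(−6) = 1.6%.

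**Step 4. Time to cross the 6 ppm threshold.** From an illustrative 20 ppm, the time is half-life × log2(20/6) = half-life × 1.74. This gives 3.5 h at a 2 h half-life and 13.9 h at 8 h. Both are well inside the 48 h window.

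**Step 5. Order of payment and verification.** The abstainer payment is due at Virtual Visit 6 and depends on biochemical verification. No CO reading is listed there, and the post-field CO reading does not exist until Lab Visit 3.

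**The case against.** The strongest case on the other side is that little rests on CO. The primary outcome and the four listed secondary outcomes are purchases made in the marketplace task at Virtual Visits 2-5, before the field week. CO is in none of the outcome lists, and the statistical analysis plan gives no model for it. This stands and limits the importance of the point. CO still matters for the adherence check and for the comparison announced under Virtual Visits 2-5.

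Four stronger inferences are tempting, and the documents do not support them.

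- **That participants go back to their usual brand and the CO contrast vanishes.** No resumption rate or distribution of gap lengths is given. The window includes same-day visits, and no passage announces a release at Virtual Visit 6. The instruction simply runs out. Participants who smoked non-menthol cigarettes in the field week were already using combusted tobacco, so a change of brand need not move CO much. Dilution is possible, but its size is unknown.
- **That the urine result is contaminated.** The urine is only banked for future analysis. The design section says lab visits serve to drop off biosamples, so a void collected on the Virtual Visit 6 morning could be handed in later. What stands is that the collection day is not fixed.
- **That the gap creates the false pass.** A participant who smoked during the week and stopped the evening before could read below 6 ppm even at a same-day visit, given the 3.5 to 13.9 h in Step 4. This is a limit of CO itself. The gap only makes it easier.
- **That a day-7 reading would measure the whole week.** It would not. By the same arithmetic it reflects recent smoking, but smoking that falls within the instructed and recorded period.

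**Conclusion.** The point holds as a measurement-timing weakness that should be fixed. The product-only instruction given at Lab Visit 2 ends at Virtual Visit 6. The only post-field CO reading follows 0 to 48 h later, and no TLFB covers that interval. For readings taken 24 h or more after Virtual Visit 6, at most 12.5% of the earlier CO excess remains, so the value mainly reflects smoking in the unrecorded gap. This rests on the assumed half-life of 2 to 8 h and on first-order decay. The conclusion is the same across that range.

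The consequences are possible misclassification in the < 6 ppm verification and possible dilution of the CO comparison by condition. The number of participants affected cannot be derived from the documents; the planned 80 completers are only an upper bound. A reader might infer that the trial's main results are at risk. They are not, because Aims 1 and 2 rest on task purchases that the gap cannot touch.

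**What to change.** 1. **Timing.** In the In-Person Lab Visit 3 section, schedule that visit on the same day as Virtual Visit 6, with CO taken before participants are released from product-only use.
2. **Fallback.** Where same-day is not possible, continue the product-only instruction until the CO reading. Add a short TLFB at Lab Visit 3 covering the time since Virtual Visit 6, including the time of the last cigarette.
3. **Verification.** Treat CO as verifying the field-week self-report only when no combusted product was used in the gap.
4. **Comparison by condition.** Keep all CO values, and add a sensitivity analysis by gap length and gap use. Do not exclude values because of gap use: that use occurs after the field condition is assigned and may depend on it, so exclusion could bias the comparison.
5. **Urine.** Define one sample: the first morning void of the Virtual Visit 6 day, handed in at Lab Visit 3. Tying it to the Lab Visit 3 morning could move collection into the gap.
6. **Reconcile.** State one start for the seven-day period, since Virtual Visits 2-5 and In-Person Lab Visit 2 differ. Align the abstainer payment with the point at which biochemical verification exists.

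The cost is less scheduling flexibility for one existing visit and a few extra minutes of interview under the fallback. No new visit, assay or participant is needed.

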2. Self-report smoking at least 5 cigarettes per day for the past year
3. Self-report smoking menthol cigarette brands > 80% of the time
4. Breathe carbon monoxide (CO) level > 8 ppm or positive urine NicCheck
5. Willingness to use other tobacco products during the study
6. Speak, comprehend, and read English sufficiently to complete study procedures
7. Have home access to a computer, smart phone, or tablet with a web camera and internet access

Exclusion criteria:

1. Currently seeking treatment to quit smoking
2. Self-reported serious medical or psychiatric condition(s) including cardiovascular and chronic respiratory diseases
3. Body temperature > 100.4 F

4. Cold, flu or COVID-19 symptoms including fever, cough, and runny nose in the past 30 days
5. Currently pregnant, breastfeeding or intending to become pregnant for the duration of the study or unwilling to agree to use adequate protection to avoid pregnancy
6. CO reading > 80 ppm
7. Enrollment stratum (Non-Hispanic, white or Black/African American)

Individuals who report smoking non-menthol flavored cigarettes will be excluded since the purpose of the trial is to understand how menthol and mint e-liquid flavor restrictions affect menthol cigarette smokers. We plan to enroll equal numbers of white and African-American/Black participants so we will exclude individuals once the stratum is full (i.e. 40 enrolled). Those with unstable medical or psychiatric conditions are excluded as these symptoms could affect a participant's ability to complete the study. We will exclude those indicating immediate readiness to stop smoking, as participation in this study may not lead to reductions in smoking. We will exclude pregnant people, those trying to become pregnant and those currently breastfeeding due to the potential harmful effects of tobacco use on developing fetuses and infants. Because participants are required to complete portions of the protocol independently during the virtual lab sessions, they will need to be able to independently read and comprehend the study materials.

Those who report past 30 day cold, flu or COVID-19 symptoms will be temporarily excluded as a safety precaution. They will be able to re-screen once they have been symptom-free for more than 30 days.

Telephone Screening Survey

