2. Minnesota Nicotine Withdrawal Scale a measure of nicotine withdrawal symptoms
3. Questionnaire of Smoking Urges-Brief – Usual Brand Cigarette, which measures the urge to smoke
4. Cigarette Evaluation Scale, which measures responses to cigarettes (e.g., reward, satisfaction)
5. Perceived Health Risks Scale, a measure of the perceived addictive potential and other health risks associated with cigarettes, e-cigarettes and nicotine gum
6. Tobacco Product Interest Scale, a visual analog scale assessing interest in use of various tobacco and nicotine products

In-Person Lab Visit 1

After completing Virtual Visit 1, participants will complete the COVID screener within 24 hours of their Lab visit via email or phone. Research staff will wear personal protective equipment including face masks and gloves. The participants will be required to wear facemasks when interacting with the staff. If participants do not have a mask, one will be provided to them to use for the remainder of the study. Temperature checks will be conducted immediately upon arrival using a thermal heat scanner.

Participants will provide carbon monoxide (CO) readings at least 6-feet away from other people, including the research staff, while they have their masks off. NicCheck Strips, which assess cotinine levels in urine, will also be used to confirm smoking status if participants have an expired breath CO reading less than or equal to 8 ppm. Participants with child-bearing potential will complete a urine pregnancy test. Participants will also be given the opportunity to sample the alternative tobacco and nicotine products that will be available during the ETM. Products include: fruit, dessert, mint, menthol, and tobacco flavored e-liquids; non-menthol preferred brand cigarettes; and mint, fruit and cinnamon flavored nicotine gum. Product sampling will occur at least 10-feet from other people, including the research staff. The sampling phase allows participants to draw upon personal experiences when completing the ETM task during Virtual Visits 2-5. This increases the study's validity by reducing the likelihood that they will purchase products from the ETM that they will not use during the field assessment and increases the likelihood of adherence to only using study products.

For the cigarettes and e-liquids, they will be instructed to take puffs ad lib for up to 2 minutes. For nicotine gum, they will be instructed to keep the product in their mouth for up to 2 minutes.

Virtual Visits 2-5

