All participants will be emailed a cessation manual and local smoking cessation resources.

Product adherence

To verify self-reported tobacco use, all used and unused products will be collected and counted at In-Person Lab Visit 3. Discrepancies between consumption stated on the TLFB versus consumption based on the products returned will be addressed. Non-adherence (i.e., using products not purchased from the ETM) will be assessed via the TLFB and qualitative interview with the importance of honest self-reporting emphasized. If participants report not using combusted tobacco, then CO readings < 6 ppm will verify their self-report.

Compensation

Participants will be paid \$155 for completing the study. They will earn \$30 for completing Virtual Visit 1, \$15 per visit for completing Virtual Visits 2-6 plus a \$50 bonus for completing the study.

Participants that do not meet enrollment criteria at Virtual 1 will earn \$20 for attending the visit. Participants that start but do not complete the study will receive payments for the virtual visits attended. They will not receive the \$50 completion bonus.

ANALYSIS PLAN

Primary Outcome

Protocol Version 10
5.13.22

- Total amount of non-menthol cigarettes purchased when menthol cigarettes are not available.

Secondary Outcomes

- Total amount of tobacco e-liquid purchased when menthol cigarettes are not available.
- Total amount of menthol e-liquid purchased when menthol cigarettes are not available.
- Total amount of mint e-liquid purchased when menthol cigarettes are not available.
- Total amount of dessert and fruit e-liquid purchased with menthol cigarettes are not available

Exploratory Outcomes

- Mean Perceived Health Risk Scale scores
- Mean Product Evaluation Scale scores
- Mean Minnesota Nicotine Withdrawal Scale scores
- Mean Questionnaire on Smoking Urges scores
- Mean Tobacco Product Interest scores
- Mean Tobacco Policy Questionnaire scores
- Total amount of non-menthol cigarettes purchased when menthol cigarettes are not available by race
- Total amount of tobacco e-liquid purchased when menthol cigarettes are not available by race.
- Total amount of menthol e-liquid purchased when menthol cigarettes are not available by race.
- Total amount of mint e-liquid purchased when menthol cigarettes are not available by race.
- Total amount of dessert/fruit e-liquid purchased when menthol cigarettes are not available by race.
- Themes emerging from the qualitative interviews

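### For participants who enter with CO below 6 ppm, a later reading below 6 ppm cannot verify no combusted use, and the payment that depends on verification is timed before that reading

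*Combined protocol and SAP*

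**What the plan says.** **Entry.** Inclusion criterion 2 asks for "Self-report smoking at least 5 cigarettes per day for the past year". Criterion 4 asks for biochemical support: "Breathe carbon monoxide (CO) level > 8 ppm or positive urine NicCheck". The In-Person Lab Visit 1 section explains the second route: NicCheck strips "will also be used to confirm smoking status if participants have an expired breath CO reading less than or equal to 8 ppm". Neither place sets a lower CO limit for that route.

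**Verification after the field week.** Under Product adherence, for participants who report no combusted tobacco, "CO readings < 6 ppm will verify their self-report". The cut-off is the same for everyone and makes no reference to the participant's own earlier CO. The same section lists the Timeline Follow Back, a count of returned products and an interview as further checks.

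**Payment.** The Virtual Visits 2-5 section covers participants who buy nothing from the marketplace and use no tobacco in the field week, with biochemical verification: "then they will receive their ETM account balance at Virtual Visit 6".

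**Order of visits.** Virtual Visit 6 is a remote visit seven days after In-Person Lab Visit 2, and no CO reading is listed for it. "In-Person Lab Visit 3 will be completed up to 48 hours after completing Virtual Visit 6", and that is where CO is read and products are counted.

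**The concern.** A verification rule is useful only if it can fail. Some participants may have CO below 6 ppm while smoking their usual amount. If such a person smokes through the field week and denies it, the later reading is still expected to be below 6 ppm, and the rule labels the denial as verified. At entry the protocol recognises that CO can miss smokers and adds a urine test for them. At the end of the field week there is no counterpart: the urine is banked for later analysis, and no immediate test is described.

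The field week is presented as the validation of the purchase task, so the verification label should mean what it says. It also bears on money, since release of the account balance depends on biochemical verification. As scheduled, that payment comes before the reading it depends on.

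**Working it through.** The plan gives no figure to reproduce here. The check compares the two thresholds, then the order of visits.

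**1. Thresholds.** Inputs: the urine route covers entry CO from 0 to 8 ppm (criterion 4; In-Person Lab Visit 1). Verification requires CO below 6 ppm (Product adherence). Assume that unchanged smoking leaves CO about where it was at entry.

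| Entry CO | Route in | Expected at In-Person Lab Visit 3 if smoking is unchanged | Can the rule catch a false report? |
|---|---|---|---|
| Above 8 ppm | CO | Above 8 ppm, not verified | Yes |
| 6 to 8 ppm | Urine | 6 to 8 ppm, not verified | Yes |
| Below 6 ppm | Urine | Below 6 ppm, counted as verified | No |

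Only the last row is a problem.

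**2. How many.** The share of participants with entry CO below 6 ppm is not in the documents. The shares below are assumptions, applied to the planned N of 80:

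- 0.05 × 80 = 4
- 0.10 × 80 = 8
- 0.20 × 80 = 16

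These are upper bounds. The rule applies only to those who also report no combusted use, so the number concerned is the overlap of the two groups. Non-menthol cigarettes are listed among the marketplace products, and a participant who buys, uses and reports them never reaches the rule.

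**3. Whether another check fills the gap.** The product count covers what was dispensed and returned; it does not directly detect cigarettes obtained elsewhere. Use of products from outside the marketplace is assessed by Timeline Follow Back and interview, both self-report. CO is the only biochemical check with a stated cut-off.

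**4. Timing.** Take In-Person Lab Visit 2 as day 0.

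- Day 0: CO reading, then products are handed out. This reading precedes field use.
- Day 7: Virtual Visit 6, the stated time of payment. No CO reading is listed.
- Up to day 7 + 2 = 9: In-Person Lab Visit 3, with the only post-field CO reading and the product count.

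The biochemical condition for payment therefore cannot be met at the stated time of payment.

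**5. What uses the verified label.** The primary and secondary outcomes are amounts purchased when menthol cigarettes are unavailable, taken from the task at Virtual Visits 2-5, before the field week. The statistical analysis plan section defines no adherence endpoint, per-protocol set or exclusion based on CO verification. The planned field comparisons between conditions concern subjective measures and change in CO itself, not the 6 ppm cut-off.

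**The case against.** The strongest reply is that little depends on this label. No primary or secondary outcome uses it, no analysis set is built on it, and CO is one of several adherence checks. That stands, and it makes this a minor point. It does not make the rule correct: a report that was never testable would still be recorded as verified.

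A second reply is that the payment text already requires verification, so the money is not due until verification exists, and the visit labels are loose. The urine sample, for instance, is to be brought both to Virtual Visit 6, which is remote, and to In-Person Lab Visit 3. This is fair. The timing problem is an inconsistency in wording, separate from the threshold problem, but it still has to be reconciled.

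A reader might infer several stronger things that the documents do not support:

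- *That everyone entering with CO of 8 ppm or less escapes the check.* Those at 6 to 8 ppm with unchanged smoking would not pass it.
- *That 4, 8 or 16 participants would be misclassified.* The shares are assumed, and only those who report no combusted use reach the rule.
- *That the payment gives participants in general a reason to deny smoking.* It goes only to those who bought nothing; someone who bought e-liquid or gum gains no balance by denying smoking.
- *That adherence can only be overstated.* The In-Person Lab Visit 2 instruction covers seven days, and CO may be read up to 48 hours after they end. A participant who complied and then smoked could fail verification, so the error can also run the other way.

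**Conclusion.** The point holds in a limited form. For participants who enter with CO below 6 ppm and report no combusted use in the field week, the stated rule cannot contradict a false report, yet counts it as verified. Their number is unknown; the counts above are ceilings on assumed shares. The reasoning also assumes that the entry reading represents the participant's usual CO, which a single reading may not.

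The consequences are confined to the verification of field-week adherence and, for participants who bought nothing, to the account-balance payment. A reader might infer that the main comparisons of marketplace conditions are at risk. They are not, because those purchases are made before the field week and do not use the check.

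The payment timing is a plain inconsistency whatever the number of low-CO entrants. The change is desirable rather than essential.

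**What to change.** 1. Under Product adherence, count CO below 6 ppm as verification only when the participant's pre-field readings at In-Person Lab Visits 1 and 2 were both 6 ppm or more. Report the remaining participants' claims of no combusted use as self-report only, and show the two groups separately.
2. Release the account balance at In-Person Lab Visit 3, after the CO reading and the product count, and amend the Virtual Visits 2-5 text to match.
3. State which period the In-Person Lab Visit 3 reading covers, and whether the product-use instruction runs to that visit, so that a participant who complied for seven days is not misclassified. State the start as well: the Virtual Visits 2-5 section counts the seven days from Virtual Visit 5, whereas the later section counts them from In-Person Lab Visit 2. This matters if the second pre-field reading is to reflect usual smoking.

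The cost is a change of wording in the protocol and analysis plan. Both pre-field CO readings are already collected, so no new visit, sample or test is needed. The downsides are small: fewer participants are labelled verified, and the balance is paid up to 48 hours later.
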